11.5 Measures of Primary and Secondary Outcomes

11.5.1 Days of Opioid Use (Healthy Living Monthly Survey)

The primary outcome of days of risky opioid use will be measured at baseline and every 30 days using items based on the Addiction Severity Index [40,41] and the COMM: "During the past 30 days, on how many days did you use [drug name]?" The question will be asked separately for heroin/illicit opioids and for nonmedical use of prescribed opioids. For patients with a current opioid prescription, items from the COMM will also be asked. To inform the primary outcome: a) "During the PAST 30 DAYS, on how many days did you need to take pain medications belonging to someone else?" and b) "During the PAST 30 DAYS, on how many days have you had to take more of your medication than prescribed?" The extent of overlap between these different types of risky use will also be measured, when applicable. The number of days of risky use for an individual will be the sum of days for each of these questions minus the overlap. Overlap between illicit use and nonmedical use will be calculated so that every individual will have a calculated number of days of risky use. To inform secondary outcomes, the following items, adapted from the COMM, will also be administered: c) "During the PAST 30 DAYS, on how many days did you borrow pain medication from someone else?" and d) "During the PAST 30 DAYS, on how many days did you use your pain medication for symptoms other than for pain (e.g., to help you sleep, improve your mood, or relieve stress)?". The assessment is self-administered using a computerized form. This approach to measuring days of drug use was used for assessing the primary outcome in the QUIT trial, where it demonstrated feasibility and sensitivity to change, including for opioid use.[21]

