7.0 EFFICACY ANALYSIS

7.1 Definition of the Primary Outcome Measure

The primary outcome (H1.1) measure is self-reported number of days of risky (illicit or nonmedical) opioid use in the past 180 days, assessed at 6 months after the baseline visit using single items based on questions used in the Addiction Severity Index (ASI) [3,4], and Current Opioid Misuse Measure (COMM) [5,6]. Participants are asked to specify the number of days of illicit opioid use and of nonmedical opioid use in the past 30 days (range is 0-30 days). Illicit opioid use includes use of heroin or synthetic opioids. Nonmedical opioid use includes using prescribed opioids more than prescribed (e.g., taking 2 tablets when the prescription indicates a dose of 1 tablet) or taking pharmaceutical opioids that were not prescribed to the individual taking them. Prescription opioids may be prescribed by the participating PCP or by another medical provider. The measure is calculated as the sum of all days of use reported on the assessments of past 30-day drug use for the first 6 months (i.e., the sum of days of use from the measures collected on day 30, day 60, day 90, day 120, day 150, and day 180).

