f) If the answer to HMPOSDNY is Yes: (HMPOSDDY) During these 30 DAYS, on how many days did you use your own prescription opioid medications more than prescribed **on the same day** that you used opioid medications that belonged to someone else? (Enter "0" for never)

For all patient participants that reported > 0 days for HMHERFYL **and** > 0 days for (HMPKOTH **or** HMRXMORE **or** HMOPINP):

g) (HMHEROPI) During these 30 DAYS, did you ever use heroin or fentanyl **on the same day** you used prescription opioid medications more than prescribed or that were not prescribed to you (including medications that belonged to someone else)? (y/n)

h) If the answer to HMHEROPI is Yes: (HMHEROOSP) During these 30 DAYS, on how many days did you use heroin or fentanyl **on the same day** you used prescription opioid medications more than prescribed, or that were not prescribed to you (including medications that belonged to someone else)? (Enter "0" for never)

Therefore, the algorithm of generating the days of risky opioid use in the past 30 days to adjust for the days of overlap when different types of risky opioid use occurred on the same day is to:

For patient participants with HMOPIRX=1:

1. Add the items (a) and (b) and subtract (e/f)
2. Add the result from #1 to (d) and subtract (g/h)

For patient participants with HMOPIRX=0:

1. Add the items (c) and (d) and subtract (g/h)

If the calculated days of risky opioid use in the past 30 days is greater than 30 based on the algorithm (e.g., due to the patient participant incorrectly completing the overlap questions), the calculated days of risky opioid use in the past 30 days will be set to 30.

When there are multiple submissions collected for HLM from the same patient participant in the same month, the data from the first submission will be used to calculate the primary outcome. If the data from the first submission is missing, the data in the second submission will be used to calculate the primary outcome. In general, the primary outcome will be calculated from the first collected non-missing data.

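### SAP 7.2.1 caps a month of risky use at 30 days but never limits the overlap it subtracts, so an over-entered overlap yields too few days and can yield zero or a negative month.

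*SAP*

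**What the plan says.** SAP 7.2.1 uses the following monthly survey items. The letters are the SAP's.

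- With a current opioid prescription: a (days using someone else's medication) and b (days taking more than prescribed), with f the days on which both occurred.
- Without a current prescription: c (days using prescription opioids not prescribed to the participant).
- Everyone: d (heroin or fentanyl days), with h the days on which d coincided with risky use of prescription opioids.
- Items e and g are yes/no gates for f and h.

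With a prescription, the rule is "Add the items (a) and (b) and subtract (e/f"), then "Add the result from #1 to (d) and subtract (g/h"). Without one, it is "Add the items (c) and (d) and subtract (g/h"). A result above 30 is corrected: "If the calculated days of risky opioid use in the past 30 days is greater than 30 based on the algorithm", then "the calculated days of risky opioid use in the past 30 days will be set to 30". The cause the SAP offers as an example is "due to the patient participant incorrectly completing the overlap questions".

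Protocol 11.5.1 gives the same construction without bounds: "The number of days of risky use for an individual will be the sum of days for each of these questions minus the overlap". SAP 7.1 gives a range for what participants are asked to enter, "nonmedical opioid use in the past 30 days (range is 0-30 days"), not for the derived value. Neither document states a lower limit for the derived month, a limit on overlap relative to its components, or a check specific to these items.

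**The concern.** The SAP intends a day with two kinds of use to count once, so the monthly value is a union of days. A union cannot be smaller than its largest member, and the overlap of two sets cannot exceed the smaller one. The SAP accepts that overlap may be answered wrongly, yet guards only against under-entry, which pushes the total up. Over-entry pushes it down, and the rule then removes days the participant has already reported.

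This is the derivation of the primary outcome. The same monthly values also feed the 90-day and 180-day sums and the longitudinal models in SAP 7.6. SAP 7.2.1 uses the first non-missing submission for a month, so a corrected resubmission would not repair the error.

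**Working it through.** **The plan's own figures.** One day of heroin and one day of own-prescription overuse, on the same day: 1 + 1 - 1 = 1, as the SAP intends. Two items of 20 days with no overlap: 20 + 20 - 0 = 40, reset to 30. For logically consistent answers the rule always returned a value between the largest item and 30 (full enumeration without a prescription, a grid with one). The fault is confined to inconsistent answers.

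**Bounds the rule should respect.**

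- Without a prescription: max(c, d) ≤ days ≤ min(30, c + d), so h ≤ min(c, d).
- With a prescription: f ≤ min(a, b), then h ≤ min(d, a + b - f).

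**Over-entered overlap, no prescription, c = 5 and d = 3 (true minimum 5).**

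| h entered | Rule gives | Truncated at min(c, d) |
|---|---|---|
| 3 | 5 | 5 |
| 5 | 3 | 5 |
| 8 | 0 | 5 |
| 10 | -2 | 5 |

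With a prescription and d = 0, a = b = 10 gives 10 + 10 - 20 = 0 for f = 20 and 10 + 10 - 25 = -5 for f = 25. The true minimum is 10.

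**How far the rule can go.** Take c and d each from 1 to 30 and h from 0 to 30: 30 × 30 × 31 = 27,900 possible answer sets. Of these, 4,960 exceed 30 and are capped. Another 17,545 fall below the larger item, including 435 that equal 0 and 4,060 that are negative. The lowest is 1 + 1 - 30 = -28. With a prescription the lowest is a = b = d = 1, f = h = 30: 3 - 60 = -57. These count possible entries; they are not expected frequencies.

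**Effect on the 180-day total.** A month scored -k makes the total negative only if the other five months sum to less than k. A month of -5 needs fewer than 5 days elsewhere. An extreme month of -28 alongside five months of 5 days gives 25 - 28 = -3; the truncated value would be 25 + 1 = 26.

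**Effect on the rate ratio.** SAP 10.0, Scenario 1, plans 180-day means of 40 (control) and 28 (STOP): 28/40 = 0.700. Assume 5% of participants lose 10 days, so an affected arm's mean falls by 0.05 × 10 = 0.5 day.

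- Both arms affected: 27.5/39.5 = 0.696.
- STOP only: 27.5/40 = 0.688.
- Control only: 28/39.5 = 0.709.

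Doubling the share or the loss gives a 1.0-day fall, and one-arm extremes of 27/40 = 0.675 and 28/39 = 0.718.

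**Monthly model.** The SAP 7.6 code fits a negative binomial distribution to each month's days. That distribution covers 0, 1, 2 and upwards, so a single negative month is invalid there, whatever the 180-day total.

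**The case against.** The strongest reply is that this is an edge case with no shown frequency. The survey is electronic and branches on earlier answers, so it may already refuse impossible overlaps. Protocol 16.3 and 16.5 promise data validation and inconsistency queries. The rule is the same in both arms, and no mechanism for a difference between arms is apparent. Items a and b go only to participants with a current prescription, and Protocol 14.3 expects 15-20% of enrolled patients to be receiving prescribed opioids. The planned control mean of 10-20 days per 90 is about 3-7 days a month, so a 10-day loss is large relative to a typical month.

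Most of this stands, and it limits the severity. It does not remove the defect. The data-checking text is general and names no check on these items. The 0-30 range describes entries. The minimum of 0 in the SAP 7.2.3 imputation code restricts imputed values, so an observed negative month would still enter the imputation model.

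A reader might infer three stronger things that the documents do not support.

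- **That heavier users are selectively under-counted.** The overlap items depend on more than one kind of use. Someone with 1 + 1 days is asked; someone with 30 days of a single kind is not.
- **That false zeros distort the post hoc zero-inflated analysis in SAP 14.1.** That model uses the 180-day total, so a month scored 0 creates a false zero only if the other five months also sum to zero.
- **That records will drop out of the primary analysis.** This needs a negative six-month total, and the documents do not say how the software would treat one.

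**Conclusion.** The derivation is wrong as written. Whenever a reported overlap exceeds the smaller of the counts it links, the rule returns fewer days than were reported, and it can return zero or a negative month. That follows from the stated arithmetic alone.

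The practical effect on the primary result is probably small. Under the assumed 5% losing 10 days, the planned ratio of 0.70 stays between 0.69 and 0.71. The error rate and the survey's entry limits are not in the documents, so neither the size nor the direction of any bias can be computed. This is a correction worth making, but not grounds to doubt the primary analysis as a whole.

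**What to change.** In SAP 7.2.1, truncate each overlap before subtracting it, taking f or h as 0 when the item is not asked or its gate is answered no:

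- With a current prescription: f* = min(f, a, b); then h* = min(h, d, a + b - f*); days = min(30, a + b - f* + d - h*).
- Without one: h* = min(h, c, d); days = min(30, c + d - h*).

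The order matters, because an untruncated f can make the bound on h negative (10 + 10 - 25 = -5).

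Two shortcuts should be avoided. A floor at zero turns negative months into false zeros and leaves 5 + 3 - 5 at 3. A floor at the largest single item matches truncation for two components but not for three. With a = b = d = 10, f = 15 and h = 0, the rule and that floor both give 15, whereas truncation gives 10 + 10 - 10 + 10 = 20.

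Apply the same derivation to the baseline value and report the number of truncated participant-months by arm. If the survey or existing code already enforces these limits, say so in SAP 7.2.1. If the analysis has been run, make this a documented correction and show the result both ways.

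The cost is a short addition to the SAP, a few lines of derivation code and one extra count. If no month is affected, no result changes.

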7.2.2 Statistical Analysis Methods for Primary Outcome

Because the most intensive intervention period is during the initial 3-4 months, the primary outcome is measured at 180 days (6 months) to capture the main intervention effect. Given the primary outcome is the number of days of risky opioid use within the first 180 days following the baseline assessment collected with HLM, a mixed effects negative binomial model with a log link will be fit to estimate the difference in means between treatment and control groups. Fixed effects include treatment effect, site effect, and the baseline value of the response variable (days of use within 30 days prior to the baseline assessment timepoint), which may improve precision. Random PCP intercepts are to account for within-PCP correlation of participant response values. Since randomization was at PCP team level where PCPs practiced in teams and shared patients regularly, PCP cluster was specified as PCP/PCP team which was the unit of randomization, that is, if two or more PCPs are randomized as a single cluster, they will be analyzed as a single cluster. Letting Y_{jk} denote the response variable of a participant in site j with PCP k , treatment denotes a binary treatment indicator variable, site denotes a multi-level categorical variable representing study sites, and baseline denote the baseline value, the formula for the log-transformed expectation of Y_{jk} is given:

$$\log[E(Y_{jk})] = \beta_0 + \beta_1 \cdot \text{treatment} + \beta_2 \cdot \text{baseline} + \beta_3 \cdot \text{site} + \gamma_k,$$

where γ_k is normally distributed with mean zero and standard deviation σ_γ representing random effect by within-PCP correlation of participant responses. The negative binomial model allows for potential overdispersion of the response variable, so is more flexible than a Poisson distribution which would require the mean to be equal to the variance.

The primary hypothesis will be evaluated by testing whether the treatment effect, β_1 , is different from zero. This is equivalent to testing whether the control mean is different from the intervention mean.

The template SAS code for the primary analysis is:

```
PROC GLIMMIX DATA=dat METHOD=quad;
  CLASS PCP treat site;
  MODEL daysin180 = treat site baseline / solution DIST=negbin LINK=log ddfm=bw;
  RANDOM intercept / SUBJECT= PCP;
RUN;
```

Where:

“dat” is the name of the dataset with one row per patient participant,

“daysin180” is the name of the primary outcome, a continuous variable indicating the number of days of risky opioid use within the first 180 days following the baseline assessment,

“treat” is a binary indicator variable coded as “1” for intervention arm STOP and “0” for control arm EUC,

“baseline” is a continuous variable indicating the number of days of risky opioid use during past 30 days prior to baseline assessment,

“site” is a categorical variable for 5 participating sites, and

“PCP” is a character variable representing PCP clusters.

The option method = quad indicates that the likelihood will be evaluated using the Gaussian quadrature method. Assessment of model fit will be reported based on standard goodness-of-fit metrics (e.g., deviance) and inspection of Pearson residuals.

The treatment effect of STOP from this model will be given as a rate ratio, the exponentiated estimate of the treatment effect, along with a 95% confidence interval. This can be interpreted as a ratio of the mean total number of days of risky opioid use for those enrolled to STOP versus EUC within the first 180 days post-randomization, when all other variables in the model are held constant. A risk ratio less than 1 would indicate fewer days of risky opioid use for those assigned to STOP compared to those assigned to EUC.

The primary outcome analysis will be performed on the Intent-to-Treat (ITT) Population, analyzing patient participants according to their PCP's randomization assignment regardless of potential exposure to the opposite assignment. The primary analysis will use multiple imputation to account for missingness of the primary outcome variable with details provided in Section 7.2.3.

7.2.3 Multiple Imputation for Missingness of the Primary Outcome

The primary outcome, number of days of risky opioid use within the first 180 days since baseline, is measured by repeated monthly assessments. For each monthly assessment, participants will record the number of days of risky use within the previous 30 days. We consider two types of missing data for this outcome:

- *Missingness due to dropout*: patient participants may withdraw early from the study and miss all subsequent monthly measurements.
- *Intermittent missingness*: patient participants may miss one or more monthly surveys, or fail to complete the opioid items on the survey, while remaining enrolled in the study.

It was anticipated during the study design stage that up to 20% of participants may be missing data for the primary endpoint due to dropout and/or nonresponse. Exclusion of those participants with missing values could lead to underestimation of variance and biased estimated parameters. Multiple imputation (MI) will be performed for the primary analysis to account for missingness of the primary outcome variable. For the sake of best practice, if a patient participant misses the response values at baseline and in each of the monthly surveys for the risky opioid use questions for all 12 post-baseline collections, the patient participant will be excluded from multiple imputation since the analysis has little or no information to inform what those actual values might have been.

Multiple imputation consists of three steps:

1. Imputation step. An 'imputation' generally represents one set of plausible values for missing data – multiple imputation represents multiple sets of plausible values. When using multiple imputation, missing values are filled in to generate multiple completed datasets.
2. Completed-data analysis (estimation) step. The desired analysis is performed separately for each dataset that is generated during the imputation step.
3. Pooling step. The results obtained from each completed data analysis are combined into a single multiple imputation result.

Data for the primary outcome analysis is collected from the HLM survey. The analysis dataset includes monthly risky opioid use in Month 1, Month 2, Month 3, ..., Month 6 for the first 6 months post-enrollment, along with baseline risky opioid use, site, treatment, and PCP cluster.

Missing patterns of the information in monthly survey for risky opioid use for the first 6 months in terms of the number and proportion will be examined and reported. The following SAS statements are used to examine the missing patterns of the data:

```
PROC MI DATA=datmiss NIMPUTE=0;  
  VAR daysinmon1-daysinmon6;  
  ODS OUTPUT missPattern=pattern;  
RUN;
```

where

“datmiss” is the name of the dataset including variables of each monthly risky opioid use for the first 6 months with one row per patient participant,

“daysinmon1-daysinmon6” are the six continuous variables indicating the number of days of risky opioid use from month1 to month6 post-baseline.

Table 2 displays an example of the dataset having 200 patient participant records outputted from the above SAS code; it is a summary of the missing data patterns for the number of days of risky opioid use for month1 to month6.

Table 2: Missing Data Patterns

Group	Daysinmon1	Daysinmon2	Daysinmon3	Daysinmon4	Daysinmon5	Daysinmon6	Freq	Percent	Group Means		
									Daysinmon1	Daysinmon2
1	X	X	X	X	X	X	160	80.0	24	21	...
2	X	X	X	X	X						
3	X	X	X	X							
4	X	X		X	X						
5		X		X	X	X					
6										
7										
8										

In the primary outcome analysis dataset, there are two types of missing data patterns: monotone missingness and non-monotone missingness.

- The monotone missingness pattern indicates if an outcome is not observed at a particular month for a patient participant, the outcome will not be observed in all subsequent months for that patient participant. Patient participants who drop-out of the study never to return to complete any of the monthly assessments are considered to have a monotone missingness pattern.
- If the pattern is not monotone, it is called non-monotone, and indicates a structure where there is no particular pattern in the missing data structure. Intermittent missingness in which patient participants miss a monthly survey but return to complete one or more other monthly surveys is considered to be non-monotone missing.

In the example in Table 2, Group 1 consists of 160 patient participants who completed the risky opioid use questions in all 6 months, which covers 80% of the total 200 observations (160/200) with a mean of 24 days of risky opioid use in month 1 and a mean of 21 days of risky opioid use in month 2. Groups 2 and 3 present two monotonic missingness data patterns in which patient participants drop out after the Month 5 and Month 4 surveys, respectively. Groups 4 and 5 present two non-monotonic missing data patterns showing intermittent missingness.

The impact of missing data depends on the missingness mechanism, of which there are three: Missing Completely at Random (MCAR), Missing at Random (MAR) and Missing Not at Random

(MNAR). In MCAR, missingness is unrelated to any measured or unmeasured characteristic, and the missing observations are a random subset of all observations. In this study, MCAR is unlikely and is not considered further. In MAR, there may be systematic differences between the missing and observed values, but they can be explained by other observed variables and with MNAR, the missingness can only be explained by unobserved data.

Five missing data patterns for risky opioid use (no missing data, intermittent missing, missing due to dropout, both intermittent missing and missing due to dropout, and all missing) will be summarized by treatment arm in the ITT population. The number and percentage of patient participants with each individual pattern and a summary of number of patient participants per pattern will be presented by treatment arm.

For CTN-0101, the following assumptions will be made:

1. For the patient participants with intermittent missingness, assume MAR.
 - While the missingness are from intermittent missingness, in which an unobserved outcome can be followed by observed outcomes since the patient participants remain in the assigned intervention group, therefore the observed outcomes can effectively predict the propensity of the missing values and the missing mechanism is missing at random (MAR).
2. For the patient participants who dropout, assume MNAR.
 - It is assumed that patient participants who drop out will have higher use after their dropout date than those who remain in the study, that is, that days of use after the withdrawal timepoint for dropouts in the treatment arm may more closely resemble that of controls than that of other treated patient participants. The values of missingness due to dropout might not retain the trend of prior observations since they are not exposed in the study environment due to various reasons, therefore the mechanism of missingness is assumed missing not at random (MNAR).

For the imputation of the primary outcome, two separate imputation procedures will be used to complete the imputation process for intermittent missingness and dropout. In the first step, the MI procedure statement uses the Markov Chain Monte Carlo (MCMC) method to impute the values of missing outcomes from intermittent missingness under the missing assumption of MAR. The variables specified in the mixed-effect regression model in Section 7.2.2, are included for imputation of primary outcome. The SAS code for imputing missing data from intermittent missingness is given below.

```
/* imputing the intermittent missingness with MAR assumption */
PROC MI DATA=datamiss nimpute=30 OUT=outimp1 SEED = 100623
min=. . 0 0 0 0 0 0
max=. . 30 30 30 30 30 30;
by treat;
mcmc impute=monotone;
VAR treat site baseline daysinmon1-daysinmon6;
RUN;
```

In this step, this MI procedure produces 30 imputed datasets by filling in the missing values from intermittent missingness with statement “impute=monotone”, and then produces the datasets as monotone missingness. The missing values due to intermittent missingness are imputed assuming that the intervention effect is still carried out while they remain enrolled in the study.

Next, MI procedure is to impute missing values from the dropouts under assumption of missing not at random (MNAR), which is a control-based pattern imputation assuming that after dropout, the unobserved values in the intervention group follow the path of observed values in control group. Based on this assumption, only the observed values in EUC group are used to derive the posterior distribution of the parameters from which the missing values in both EUC and STOP group are imputed. This approach is conservative as it tends to reduce the difference between STOP group and EUC group. The SAS code for imputing missing data from dropout is given below.

```
/* imputing the dropouts with MNAR assumption */
PROC MI DATA=outimp1 nimpute=1 OUT=outimp2 SEED = 100623
min=. . 0 0 0 0 0 0
max=. . 30 30 30 30 30 30;
CLASS treat site;
VAR treat site baseline daysinmon1-daysinmon6;
monotone REG;
MNAR model(daysinmon1-daysinmon6/ modelobs=(treat="0"));
RUN;
```

As the 30 completed datasets are generated, analyses of the 30 imputed datasets using the standard procedure for the mixed effects negative binomial model are performed separately for each imputed dataset using “by _imputation” statement.

```
/* analysis model */
PROC GLIMMIX DATA = outmi NOCLPRINT;
BY _imputation_;
CLASS PCP treat site;
MODEL daysin180 = treat site baseline / DIST=negbin LINK=log;
RANDOM intercept / SUBJECT = PCP;
LSMEANS treat / pdiff ILINK;
ODS OUTPUT PARAMETERESTIMATES=GPARMS;
RUN;
```

To draw statistical inference based on the results from the 30 imputations, the combination rules are applied in MIANALYZE procedure [7, 8]. Proc MIANALYZE is set to estimate the pooled variance from two components: within-imputation variance and between-imputation variance. Within-imputation variance is the average of the mean of the within variance estimate in each imputed dataset. Between-imputation variance reflects the extra variance due to the missing data, which is estimated by taking the variance of parameter of interest estimated over imputed datasets. Simulations indicate that the 30 imputations will produce enough efficiency to avoid diminishing power for detection of the treatment effect [9].

```
/* pooling the individual estimates from each imputed datasets into one set of estimates*/
PROC MIANALYZE PARMS=mixparms;
CLASS visno;
MODELEFFECTS intercept treat site baseline;
RUN;
```

Statistical inferences of the treatment effect will be presented as the rate ratio along with its 95% confidence interval adjusting for site effect and the values of risky opioid use within 30 days prior to the baseline assessment based on the combination of the 30 imputed datasets.

